#### **PASI 50 Responders**

Participants with  $\geq 50\%$  improvement in PASI from baseline will be considered PASI 50 responders.

#### **PASI 75 Responders**

Participants with  $\geq 75\%$  improvement in PASI from baseline will be considered PASI 75 responders.

#### **PASI 90 Responders**

Participants with  $\geq 90\%$  improvement in PASI from baseline will be considered PASI 90 responders.

#### **PASI 100 Responders**

Participants with a PASI score of 0 will be considered PASI 100 responders.

### 5.3.2. Estimands

**Primary Trial Objective:** To evaluate whether the oral tablet formulation of JNJ-77242113 will result in superior efficacy compared with placebo in participants with moderate-to-severe plaque psoriasis.

**Estimand Scientific Question of Interest:** What is the proportion of participants considered to have benefited from JNJ-77242113 versus placebo assessed by the PASI75 response at Week 16?

#### 5.3.2.1. Primary Estimand

The primary estimand, based on the above primary objective, is defined by the following 5 attributes which assess the treatment effects not only based on the variable measurements, but also based on intercurrent events:

**Study intervention:**

- JNJ77242113 10 mg **CCI** oral delayed release tablet administered once a day.
- JNJ77242113 50 mg **CCI** oral delayed release tablet administered once a day.
- Placebo, oral tablet administered once a day.

**Population:** adult participants with moderate to severe psoriasis

**Variable/endpoint:** Binary response variable, where a responder is defined as a participant achieving a PASI75 response at Week 16. A participant with an intercurrent event in categories 1-2 defined below will be considered as a non-responder.

**Intercurrent Events (ICEs) and their corresponding strategies.**

| ICEs  | Analysis Strategy for Addressing Intercurrent Events  |
|---|---|
| 1. Discontinuation of study intervention due to lack of efficacy, or an AE of worsening of psoriasis prior to Week 16       | Composite Strategy: Participants with these intercurrent event are considered as non-responders. The occurrence of these intercurrent event being captured in the variable definition. |
| 2. Initiation of a protocol-prohibited medication or therapy during the study that could improve psoriasis prior to Week 16 |   |
| 3. Discontinuation of study intervention for reasons other than ICE 1   | Treatment Policy: observed data will be used regardless of whether or not this intercurrent event had occurred.  |

For participants experiencing multiple ICEs, ICE 2 will override ICE 3.

A list of Participants who experienced ICEs 1-3 will be provided.

**Population level summary:** Difference in the proportions of participants achieving a PASI 75 responses at Week 16 between the treatment groups.

### 5.3.2.2. Supplementary Estimands

#### 5.3.2.2.1. Supplementary Estimand 1 (Hypothetical Estimand):

In this supplementary estimand, the only component that changes from the definition of the primary estimand is the hypothetical strategy will be used for addressing ICEs 1-3.

**Hypothetical strategy:** assess the treatment effect as if the intercurrent event would not have occurred. Under the hypothetical strategy, data collected after ICEs 1-3 will not be used in analysis and will be imputed using a MAR multiple imputation method.

#### 5.3.2.2.2. Supplementary Estimand 2 (Treatment Policy Estimand):

This supplementary estimand has the same components as the primary estimand, except for the strategies used for ICEs 1-3.

**Treatment policy strategy:** assess the treatment effect regardless of whether or not intercurrent events had occurred. Under the treatment policy strategy, observed data collected after ICEs will be used in analysis.

### 5.3.3. Analysis Methods

#### 5.3.3.1. Analysis Methods for the Primary Estimand

The primary endpoint will be analyzed based on the primary estimand and the data from all participants in FAS will include data from all randomized participants who received at least one administration of study intervention based on their assigned intervention group, regardless of the actual intervention received.

Comparisons of each JNJ-77242113 treatment group versus the placebo group will be performed for the primary endpoint of PASI 75 at Week 16. The Cochran-Mantel-Haenszel chi-square statistic stratified by baseline weight category ( $\leq 90$  kg,  $> 90$  kg) at a 2-sided significance level of 0.1 will be used. Difference in response rates between each of the active groups and the placebo group adjusted for baseline weight category ( $\leq 90$  kg,  $> 90$  kg) using Mantel-Haenszel weight and the corresponding 90% CI will be presented. Pairwise comparisons will not be adjusted for multiplicity.

Participants with ICEs 1-2 before Week 16 will be considered as PASI75 non-responders at Week 16. Participants with ICE 3, observed PASI data after this ICE will be utilized in the analysis. After accounting for the ICEs for the primary estimand, participants with the missing data of the primary endpoint at Week 16 will be considered as non-responders.

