## 9.4. Statistical Analyses

### 9.4.1. General Considerations

An overall Type I error rate of 0.10 (2-sided) will be used for statistical testing. No multiplicity control methods will be applied to the secondary endpoints in this Phase 2a study. Nominal p-values will be calculated for all comparisons. Descriptive summary statistics, such as n, mean, standard deviation (SD), median, interquartile range, minimum, and maximum for continuous variables, and counts and percentages for discrete variables will be used to summarize most data.

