## 1.2. Study Design

This is a randomized, double-blind placebo-controlled, parallel, multicenter, interventional study in participants with moderate-to-severe plaque psoriasis. This Phase 2a study is focused on proof of-concept and will assess the efficacy, safety, and tolerability of JNJ-77242113 (an IL-23R peptide antagonist) orally administered as a delayed release tablet formulated with an CCI [REDACTED]

[REDACTED] This study will be conducted in parallel with the complementary study 77242113PSO2001, a Phase 2b randomized, double-blinded, dose-ranging, placebo-controlled study designed to evaluate the efficacy and safety of JNJ-77242113, formulated as an immediate-release oral tablet CCI [REDACTED] in adults with moderate-to-severe plaque psoriasis. The target population for this study intervention consists of participants 18 to 75 years of age (or the legal age of consent if it is higher in the jurisdiction in which the study is taking place), with moderate to severe psoriasis of at least 26 weeks duration, primarily defined as a total BSA  $\geq 10\%$ , total PASI  $\geq 12$ , and total Investigator Global Assessment (IGA)  $\geq 3$  at screening and baseline.

A target of 80 participants will be enrolled in this study. Participants will be randomized to receive 1 of the 2 JNJ-77242113 doses of an oral delayed release tablet CCI [REDACTED] or placebo in a 3:3:2 ratio (30:30:20) using dynamic central randomization, stratified by baseline weight ( $\leq 90$  kg,  $>90$  kg).

The treatment arms for this study will be as follows:

**Group 1:** 10 mg JNJ-77242113 oral delayed release tablet CCI [REDACTED] administered once daily from Week 0 through Week 16.

**Group 2:** 50 mg JNJ-77242113 oral delayed release tablet CCI [REDACTED] administered once daily from Week 0 through Week 16.

**Group 3:** Placebo oral delayed release tablet, administered once daily from Week 0 through Week 16.

[figure not shown]

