## 3. SAMPLE SIZE DETERMINATION

This study is designed to assess the clinical response, safety/tolerability, and pharmacology of JNJ-77242113 CCI in participants with moderate-to-severe plaque psoriasis. The sample size is evaluated based on the primary endpoint of a PASI 75 response at Week 16. The sample size of 80 participants was chosen in order to have sufficient power to detect a difference between the JNJ-77242113 CCI (30 participants for each of low and high dose groups) and the placebo group (20 participants).

The assumptions for the sample size and power calculations were mainly based on the clinical data from guselkumab Phase 3 clinical studies that evaluated the safety and efficacy in the treatment of adult participants with moderate-to-severe plaque psoriasis.

The null hypothesis is to be tested at an overall Type 1 error rate of 0.10 (2-sided). Assuming PASI75 response rates at Week 16 are 5% to 10% for placebo and 40% to 80% for JNJ-77242113 CCI, a sample size of 20 participants in the placebo group and 30 participants in the JNJ-77242113 CCI will provide at least 90% power to detect a 35% difference between the JNJ-77242113 CCI and placebo groups in the proportion of participants achieving a PASI 75 response at Week 16 based on a 2-sample Z-test.

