## 5. STATISTICAL ANALYSES

### 5.1. General Considerations

Unless specified otherwise, efficacy data summaries will be provided by intervention group for FAS. Data primarily will be summarized using descriptive statistics. Continuous variables will be summarized using the number of observations, mean, SD, median, interquartile range, minimum and maximum, as appropriate. Categorical values will be summarized using the number of observations and percentages as appropriate. In addition, graphical data displays (eg, line plots) and participant listings may also be used to summarize/present the data.

For binary response efficacy endpoints, comparisons between each of the JNJ-77242113 CCI groups versus placebo will be performed using a Cochran-Mantel-Haenszel (CMH) test stratified by the baseline weight ( $\leq 90$  kg,  $>90$  kg). For continuous efficacy endpoints, treatment comparisons will be performed using a Mixed-Effect Model Repeated Measure (MMRM) model. The MMRM model will have factors for treatment group, baseline weight ( $\leq 90$  kg,  $>90$  kg), baseline value for the corresponding efficacy endpoint, visit, and treatment group by visit interaction. An unrestricted (UN) variance-covariance matrix for repeated measures within a participant will be used. If the model with unstructured covariance structure does not converge, alternative covariance structures

will be considered in the following order, with the first structure that converges being used in the analysis: heterogeneous Toeplitz, standard Toeplitz, and autoregressive of order 1.

The Least Square mean (LSmean) estimates and their corresponding 90% confidence interval (CI) will be provided at each time point. In addition, the estimates of LSmean difference and 90% CIs between the JNJ-77242113 groups and placebo will be provided.

In general, all statistical tests will be performed at a 2-sided significance level of  $\alpha=0.10$ . Nominal p-values will be reported. No multiplicity adjustment is planned for this phase 2a proof-of-concept study.

The baseline measurement is defined as the closest measurement taken prior to or at the time of the first study agent administration date unless otherwise specified.

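### The 0.10 that protocol and SAP call an overall Type I error is a per-comparison level; with two unadjusted dose comparisons the family-wise rate is about 0.17 two-sided, or about 0.084 for false superiority.

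*SAP*

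**What the plan says.** **Error rate.** Protocol 9.4.1 says: "An overall Type I error rate of 0.10 (2-sided) will be used for statistical testing". The synopsis (protocol 1.1) repeats this, and the sample size sections (protocol 9.2 and SAP 3) also call the 0.10 overall.

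**Primary test.** SAP 5.3.3.1 says: "Comparisons of each JNJ-77242113 treatment group versus the placebo group will be performed for the primary endpoint of PASI 75 at Week 16". The stratified Cochran-Mantel-Haenszel (CMH) statistic "at a 2-sided significance level of 0.1 will be used", followed by "Pairwise comparisons will not be adjusted for multiplicity". SAP 1.2 gives the allocation: "or placebo in a 3:3:2 ratio (30:30:20) using dynamic central randomization". Both comparisons therefore share 20 placebo participants.

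**Multiplicity.** In the protocol the waiver is limited: "No multiplicity control methods will be applied to the secondary endpoints in this Phase 2a study" (9.4.1). The SAP makes it general: "No multiplicity adjustment is planned for this phase 2a proof-of-concept study" (5.1). Both sections call the p-values nominal. SAP Appendix 2, where changes to protocol-planned analyses belong, reads N/A.

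**Hypothesis and power.** Protocol 9.1 and SAP 2 state one hypothesis: the tablet is superior to placebo on PASI 75 at Week 16. Neither says whether one dose or both must succeed. Protocol 9.2 and SAP 3 claim at least 90% power for a 35-point difference by a two-sample Z-test, with placebo at 5% to 10% and active at 40% to 80%.

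**The concern.** An overall error rate belongs to the whole set of primary tests. Two unadjusted tests at 0.10 do not have an overall rate of 0.10 unless something else restores it, such as a testing order, a gatekeeping rule or a requirement that both doses win. I found none of these in either document.

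The protocol's wording makes matters worse. By waiving control for secondary endpoints only, it suggests that the primary comparisons are covered by the overall 0.10. The SAP removes that cover and records no change.

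What is at stake is how a Week 16 result is read. If one dose reaches p < 0.10, a reader of the protocol would credit the finding with an error rate that the procedure does not have. The shared placebo group also links the two tests: an unusually low response among 20 people favours both doses at once.

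**Working it through.** **1. The plan's own power figure.** Inputs from SAP 3: 20 placebo, 30 active, two-sided 0.10 (critical value 1.645), 35-point difference. With unpooled variance, power = Φ(Δ/SE − 1.645), where SE = √(p0(1−p0)/20 + p1(1−p1)/30).

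- 5% vs 40%: SE = √(0.002375 + 0.008) = 0.1019; 0.35/0.1019 − 1.645 = 1.79; power 0.963.
- 10% vs 45%: SE = √(0.0045 + 0.00825) = 0.1129; 0.35/0.1129 − 1.645 = 1.45; power 0.927.

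Exact binomial enumeration of the pooled Z-test gives 0.948 and 0.902. The claim of at least 90% therefore reproduces when the full 0.10 is spent on one comparison. The pooled normal approximation gives 0.918 and 0.876; the documents do not say which variant was used.

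**2. Correlation of the two tests.** Under the null with common variance, the shared placebo group gives ρ = 30/(30 + 20) = 0.6.

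**3. Family-wise error, large sample.** Assume that neither dose works and that success means at least one dose significant. For a bivariate normal with ρ = 0.6, the probability that both statistics exceed +1.645 is 0.0155.

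- Superiority direction: 0.05 + 0.05 − 0.0155 = 0.0845.
- Either direction: 2 × 0.0845 = 0.169; the overlap of opposite-direction rejections is negligible.
- For comparison: independent tests would give 1 − 0.9² = 0.19, and the Bonferroni bound is 0.20.

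**4. Family-wise error, exact at 20/30/30.** Sum over the placebo count the probability of that count times 1 − (1 − r)², where r is the rejection probability of one comparison given that count (unstratified test).

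| Common response rate | Either direction | Superiority, at least one dose |
|---|---|---|
| 5% | 0.151 | 0.043 |
| 10% | 0.186 | 0.086 |
| 20% | 0.186 | 0.093 |
| 30% | 0.178 | 0.092 |

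A simulated weight-stratified CMH test (400,000 runs, two equal strata assumed) gives 0.151, 0.184 and 0.173 in either direction at 5%, 10% and 20%. In the superiority direction it gives 0.042, 0.084 and 0.079.

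**5. What holding 0.10 overall would cost.**

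| Procedure | Exact power, 5% vs 40% | Exact power, 10% vs 45% |
|---|---|---|
| Per-comparison 0.10, as planned | 0.948 | 0.902 |
| Dunnett-type, 0.0575 each | 0.882 | 0.810 |
| Bonferroni, 0.05 each | 0.860 | 0.792 |
| Fixed sequence, first dose | 0.948 | 0.902 |
| Fixed sequence, second dose (both doses equally effective) | 0.910 | 0.841 |

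If the dose tested first reaches 60%, the dose tested second has power 0.948 and 0.898, close to the unadjusted values.

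**The case against.** The strongest reply is that nothing is hidden. SAP 5.1 says that no multiplicity adjustment is planned for a proof-of-concept study and that p-values are nominal. Protocol 9.4.1 calls the p-values nominal for all comparisons, and protocol 9 defers detail to the SAP. Unadjusted testing is a legitimate choice at this phase. That stands: the choice is defensible and the SAP discloses how the tests are run. It does not rescue the word *overall*.

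Three stronger readings are tempting, and the documents do not support them.

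- *A reader might infer a 17% chance of a falsely positive study.* The 0.169 includes results in which a dose is significantly worse than placebo. The hypothesis is superiority, and in that direction the figure is 0.084, to be set against 0.05. At a 5% null rate the exact value is 0.043, below 0.05, and most of the 0.151 lies in the wrong direction.
- *A reader might take 0.17 as a fixed property of the plan.* It follows only if one significant dose is enough, and the plan states no such rule. If both doses had to win, exact false superiority would be 0.001 to 0.021 at the same four response rates.
- *A reader might infer that the power claim is wrong.* It matches the 0.10 per-comparison test in SAP 5.3.3.1. Only its pairing with an overall error rate is wrong.

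It is also fair to say that imposing a testing order would be a trade-off rather than a correction: the second dose can fall below the 90% for which both dose groups were sized.

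**Conclusion.** The point holds as an error of statement, in four places, about the primary analysis. The 0.10 is the level of each comparison, and so is the stated power. Under an at-least-one-dose rule the family-wise two-sided error is about 0.17 (exact 0.15 to 0.19), and false superiority is about 0.084 against 0.05 (exact 0.043 at a 5% null rate, 0.086 to 0.093 at 10% to 30%).

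These figures assume that neither dose works, a common response rate in all groups, the full 20/30/30 participants and, for the exact values, no stratification. The Week 8 interim is not counted: it uses another time point, and SAP 5.8 plans no change to the study from it.

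The documents do not support the inference that the plan must adjust. They support the requirement that the label and the procedure agree, and that the SAP record where it goes beyond the protocol's waiver.

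**What to change.** 1. In protocol 1.1, 9.2 and 9.4.1 and in SAP 3, replace *overall* with *per-comparison*.
2. In the same places, say that the power of at least 90% is per comparison. Give the family-wise rate for at least one significant dose: about 0.17 two-sided, about 0.084 in the superiority direction.
3. In SAP Appendix 2, replace N/A with an entry stating that non-adjustment extends from the secondary endpoints to the two primary comparisons.

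These are wording changes. They do not affect design, sample size, conduct or power.

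If the sponsor prefers to keep an overall 0.10, SAP 5.3.3.1 must name a controlling procedure before unblinding. A fixed sequence of the two doses would do: the second is declared significant only if the first is, each at two-sided 0.10, with both nominal p-values still reported. The first test loses nothing. The second loses some power, for example from 0.902 to 0.841 when both doses are at 45% against 10%. Splitting the level equally would cost more, as the working shows.

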#### 5.3.3.2. Additional Analysis for the Primary Estimand

The primary estimand for the completers will be analyzed using the Cochran-Mantel-Haenszel statistic stratified by baseline weight category ( $\leq 90$  kg,  $> 90$  kg).

### 5.3.3.3. Analysis for Supplementary Estimands

The analyses specified below for supplementary estimands will be applied for the primary endpoint.

#### 5.3.3.3.1. Supplementary Analysis 1 (Hypothetical Estimand)

Under this estimand, PASI 75 response will be considered missing after an intercurrent event and missing data will be imputed using multiple imputations (MI) by fully conditional specification (FCS).

More specifically, the missing PASI75 responses will be imputed with FCS logistic regression including treatment group, baseline PASI score, and PASI75 response status through Week 16 in the model with seed = 789 and 500 imputations. The proportion difference of PASI75 response between each JNJ-77242113 group and placebo group at Week 16 adjusted for baseline weight category ( $\leq 90$  kg,  $> 90$  kg) using Mantel-Haenszel weight and its 90% CI combining multiple datasets will also be provided. A CMH test stratified by baseline weight category ( $\leq 90$  kg,  $> 90$  kg) will be used to obtain the CMH statistic for each imputed dataset.

The values of the general association test statistics from the CMH test for each imputed dataset will be transformed using the Wilson-Hilferty transformation to create a more normal distributed statistic:

$$Z = \frac{(CMH)^{(1/3)} - 7/9}{(2/9)^{(1/2)}}.$$

The resulting transformed values will be combined using SAS PROC MIANALYZE and obtain the overall p-value for the CMH test. Difference in PASI75 response rates at Week 16 between each of the active intervention groups and the placebo group at Week 16 adjusted for baseline weight category using Mantel-Haenszel weight and its 90% CI combining multiple datasets will also be provided.

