Participants who decide to discontinue study intervention administration for reasons other than those outlined above must be interviewed by the investigator to determine if a specific reason for discontinuing study intervention can be identified. Participants should be explicitly asked about the possible contribution of AEs to their decision to discontinue study intervention; investigators should confirm that any AE information elicited has been documented. If a participant elects to discontinue study intervention due to an AE, the event should be recorded as the reason for study intervention discontinuation, even if the investigator's assessment is that the AE would not require study intervention discontinuation. The reason for study intervention discontinuation must be documented in the eCRF and in source documents. Study intervention assigned to a participant who discontinues may not be assigned to another participant.

A participant will not be automatically withdrawn from the study if they must discontinue treatment before the end of the treatment regimen. Participants who discontinue study intervention but do not terminate study participation will continue to return for protocol-specified procedures and evaluations for approximately 4 weeks following the last administration of study intervention. Participants who terminate study intervention early should return for an early termination visit as soon as possible after discontinuing study intervention and return for the final follow-up visit approximately 4 weeks after their last administration of study intervention. More details will be provided in the eCRF completion guidelines.

All procedures and evaluations must be conducted prior to a participant's withdrawal of consent.

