#### 5.3.3.3.2. Supplementary Analysis 2 (Treatment Policy Estimand)

The primary endpoint will also be analyzed utilizing the treatment policy estimand. For participants who experience an intercurrent event through Week 16, the analysis will be performed using observed data regardless of intercurrent events. Missing data will be imputed using multiple imputation method specified in Section 5.3.2.2.1.

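### The multiple-imputation model for the supplementary PASI 75 analyses omits baseline weight category, although the imputed data are then analysed within weight strata

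*SAP*

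**What the plan says.** Randomisation is done "using dynamic central randomization, stratified by baseline weight" (SAP 1.2), and Protocol 6.3 names no other stratification factor.

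For Supplementary Estimand 1, SAP 5.3.2.2.1 states that "data collected after ICEs 1-3 will not be used in analysis and will be imputed using a MAR multiple imputation method". The model is given in SAP 5.3.3.3.1: "the missing PASI75 responses will be imputed with FCS logistic regression including treatment group, baseline PASI score, and PASI75 response status through Week 16". The same section then prescribes, for each imputed dataset, "A CMH test stratified by baseline weight category", together with a Mantel-Haenszel difference adjusted for weight category and its 90% CI.

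Supplementary Analysis 2 keeps data observed after intercurrent events and fills only what is missing: "Missing data will be imputed using multiple imputation method specified in Section 5.3.2.2.1" (SAP 5.3.3.3.2). SAP 5.4.1.3 and 5.4.2.1.1 carry both supplementary analyses to PASI 90, PASI 100, IGA 0/1 and IGA 0.

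Two other rules serve for comparison. In the primary analysis (SAP 5.3.3.1), "participants with the missing data of the primary endpoint at Week 16 will be considered as non-responders", so no imputation model is involved. The MMRM for continuous endpoints (SAP 5.1 and 5.4.2.2) includes baseline weight category.

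**The concern.** An imputation model should contain at least the variables on which the later analysis conditions. Here it does not. Missing responses are drawn as if weight carried no information once arm, baseline PASI and PASI 75 status are known, and the completed data are then split by weight. A heavier participant with a missing response is imputed from a mixture of lighter and heavier participants in the same arm.

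The plan also rests on two different missing-at-random assumptions without giving a reason: conditional on weight in the MMRM, not conditional on weight in the imputation for binary endpoints. The supplementary analyses are there to test robustness, so an avoidable bias of unknown sign works against their purpose.

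**Working it through.** **The plan's own figure.** The SAP gives no figure for the imputed analyses. The nearest is the power statement in SAP 3: at least 90% for a 35-point difference, 20 placebo v 30 active, two-sided α = 0.10, two-sample Z-test. With an unpooled variance:

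- 5% v 40%: SE = √(0.05×0.95/20 + 0.40×0.60/30) = 0.102; power = Φ(0.35/0.102 − 1.645) = 96.3%.
- 10% v 45%: SE = √(0.10×0.90/20 + 0.45×0.55/30) = 0.113; power = 92.7%.

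The statement reproduces in this form. With a pooled variance the figures are 91.8% and 87.6%. The SE of about 11 points is the yardstick used below; it gives a 90% CI half-width of 1.645 × 11.3 = 18.6 points.

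**Size of the bias, closed form.** Let w be the share >90 kg, pL and pH the active response rates in the lighter and heavier strata, and mL and mH the shares imputed. If imputation ignores weight, the large-sample bias in the active response rate is

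[(1−w)(1−mL)pL + w(1−mH)pH] / [(1−w)(1−mL) + w(1−mH)] − [(1−w)pL + w·pH],

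which simplifies to w(1−w)(mH−mL)(pL−pH) / [1 − (1−w)mL − w·mH].

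The numerator is a product, so both conditions are needed: unequal imputed shares and unequal response. With the arms balanced on weight and no bias in placebo, this is also the bias in the Mantel-Haenszel difference. All inputs are assumptions: w 30% to 50%, active response 30% to 70% by stratum, imputed share 5% to 30% by stratum.

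| w | pL / pH | mL / mH | Bias (points) |
|---|---|---|---|
| 0.3 | 70% / 50% | 5% / 15% | +0.5 |
| 0.5 | 70% / 50% | 5% / 15% | +0.6 |
| 0.5 | 70% / 50% | 10% / 30% | +1.25 |
| 0.5 | 70% / 30% | 10% / 30% | +2.5 |
| 0.5 | 60% / 60% | 10% / 30% | 0 |
| 0.5 | 50% / 70% | 10% / 30% | −1.25 |
| 0.5 | 70% / 50% | 10% / 10% | 0 |

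Worked example, third row: 0.25 × 0.20 × 0.20 / 0.80 = 0.0125. With a response gap of only 10 points (65% v 55%, heavier imputed more) the formula gives about +0.2 to +0.6.

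**Simulation with earlier PASI 75 status in the model.** The closed form ignores the information carried by earlier visits. A simulation with N = 4,000 used 45% >90 kg, placebo response 8% with 15% imputed, visits at Weeks 4, 8, 12 and 16, and 10% of lighter and 30% of heavier active participants imputed. Sequential logistic imputation gave these biases in the Mantel-Haenszel difference (Monte Carlo SE about 0.1 point):

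| pL / pH | Weight omitted | Weight included |
|---|---|---|
| 70% / 50% | +0.9 | +0.1 |
| 70% / 30% | +1.8 | +0.2 |
| 60% / 60% | −0.1 | −0.2 |
| 50% / 70% | −1.1 | −0.3 |

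Where the closed form is non-zero the signs agree, and including weight removes most of the bias; residuals of up to 0.3 point remain in this simulation.

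**At trial size (30 v 20).** In the same four scenarios, omitting weight rather than including it moved the estimate by +0.8, +1.2, +0.4 and −0.5 points. This run needed mild ridge shrinkage to avoid separation, so only the contrast between the two models is read. The +0.4 at equal response shows that these contrasts are themselves imprecise.

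**Scale.** 1.25 points is 0.11 SE, or 0.0125 × 30 = 0.4 of a participant. 2.5 points is 0.22 SE, or 0.75 of a participant.

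**The case against.** The case for leaving the model alone has four parts.

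- **Direction.** A reader might infer that more intercurrent events among heavier active participants would by themselves favour active drug. They would not: weight must also predict response given the other covariates, with heavier participants responding less. The documents give no response rate and no event rate by weight. This stands, and the point is worded accordingly.
- **Reason for the stratum.** A reader might also infer that weight was chosen as stratum because it affects response. Neither document says so. The plan looks at response by weight (SAP 5.5.2.2.1, 5.5.2.2.2, 5.7.5) and concentrations by weight (5.7.1.1), but asserts no effect or direction. This stands too.
- **Scope and size.** The primary analysis and the main secondary analyses use non-responder imputation. P-values are nominal, and the bias is a small fraction of the SE. In Supplementary Analysis 2 an intercurrent event alone triggers no imputation. All true, with one qualification: after early discontinuation, participants return for "evaluations for approximately 4 weeks following the last administration of study intervention" (Protocol 7.1), so Week 16 values may well be missing there.
- **Parsimony.** PASI is scored at six post-baseline visits through Week 16 (Protocol 1.3), and only 20 × 5% = 1 to 20 × 10% = 2 placebo responders are expected. Each extra term raises the risk of separation, and earlier PASI 75 status already carries part of any weight effect. This is a fair cost, but it does not justify leaving out the one factor on which the analysis is stratified.

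**Conclusion.** The inconsistency is on the page: the imputation model omits a variable that the analysis conditions on, while the MMRM includes it. Its consequence is conditional. For response gaps of 20 to 40 points between strata and imputed shares differing by 10 to 20 points, the bias is about 0.5 to 2.5 points in either direction. It is zero in large samples if weight does not predict response given the other covariates, or if the imputed shares are equal. Every rate behind these figures is an assumption.

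The documents do not support a reading that the trial's result is tilted toward active drug. The primary analysis is unaffected, and the supplementary analyses move little beside an SE of about 11 points. This is a low-priority improvement, worth making because the sign cannot be known in advance and the change is small.

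**What to change.** In SAP 5.3.3.3.1, add baseline weight category (≤90 kg, >90 kg) to the covariates of the FCS logistic model. Point 5.3.3.3.2 and 5.4.2.1.1 to that section; they now cite 5.3.2.2.1 and 5.3.2.2.2, which define the estimands but specify no imputation model.

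The stratum is collected at randomisation, so no new data are needed. The cost is one further coefficient in each visit's imputation model, with a slightly higher risk of separation given the few placebo responders expected.
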